4.4.1.4 Pertussis Vaccine Seroresponse

The derived Pertussis vaccine seroresponse indicator will be taken as “Yes” if:

When assessing the immunogenicity after 3rd dose of Pentacel® vaccine

- Pre-1st vaccination concentration < LLOQ, then post-3rd vaccination concentration should be $\geq 4x$ the LLOQ
- Pre-1st vaccination concentration \geq LLOQ but < 4x the LLOQ, then post-3rd vaccination concentration should achieve a 4-fold rise (post-3rd vaccination/ pre-1st vaccination ≥ 4)
- Pre-1st vaccination concentration $\geq 4x$ the LLOQ, then post-3rd vaccination concentration should achieve a 2-fold response (post-3rd vaccination/ pre-1st vaccination ≥ 2)

When assessing the immunogenicity after 4th dose of Pentacel® vaccine

- Pre-booster (4th) vaccination concentration < LLOQ, then post- booster (4th) vaccination concentration should be $\geq 4x$ the LLOQ
- Pre-booster (4th) vaccination concentration \geq LLOQ but < 4x the LLOQ, then post- booster (4th) vaccination concentration should achieve a 4-fold rise (post-4th vaccination/ pre-4th vaccination ≥ 4)
- Pre- booster (4th) vaccination concentration $\geq 4x$ the LLOQ, then post- booster (4th) vaccination concentration should achieve a 2-fold response (post-4th vaccination/ pre-4th vaccination ≥ 2)

4.4.2 Safety

4.4.2.1 Solicited Reactions

4.4.2.1.1 Daily Intensity

All daily records for solicited reactions will be derived into daily intensity according to the following classification: None, Grade 1, Grade 2, Grade 3, or Missing (Unknown).

For the derivation of daily intensities, the following sequential steps will be applied:

- 1) Solicited reactions (except Fever/Pyrexia) with an investigator presence recorded as “No” and with all daily records missing, then all daily intensities will be derived as None.
- 2) For non-measurable (NM) solicited reactions, daily intensities will correspond to daily records reported in the clinical database. For measurable solicited reactions the daily measurements reported in the clinical database will be converted based upon the intensity scales defined in the protocol; this assumes a reaction that is too large to measure (NM) is Grade 3. Note the intensity could be considered “None” (not a reaction) in the analysis despite being considered a reaction by the investigator.

Note: The maximum intensity on the ongoing period is derived from the record of the maximum intensity/measurement after the end of the solicited period following the rule described above.

4.4.2.1.2 Maximum Overall Intensity

Maximum overall intensity is derived from the daily intensities as described in [Section 4.4.2.1.1](#) and is calculated as the maximum of the daily intensities over the period considered.

4.4.2.1.3 Presence

Presence is derived from the maximum overall intensity on the period considered:

- None: No presence
- Grade 1, Grade 2, or Grade 3: Presence
- Unknown: Missing presence

Subjects with at least one non-missing presence for a specific endpoint will be included in the analysis. Conversely, those without a non-missing presence will not be included in the analysis of the endpoint.

The time period is displayed as D0-D3, D4-D7, D8 and later.

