#### **Visit 6 (15 to 18 months of age): Collection of Safety Information, Blood Sample, and Vaccination**

- 1) Collect and review the diary card (DC5) with the parent / guardian, including any AEs, medications, or therapy that occurred since vaccination. If an SAE, including an AESI, has occurred, follow the instructions in [Section 10](#) for reporting it.
- 2) Review temporary contraindications for blood sampling. Ensure the subject has not had any antibiotics within the previous 72 hours (3 days).
- 3) Collect 5 mL of blood (BL3) (see [Section 7](#) for detailed instructions regarding the handling of blood samples).
- 4) Review warnings and precautions to vaccinations.
- 5) Review contraindications to subsequent vaccinations and conditions for withdrawal.
- 6) Measure temperature. If the temperature is  $\geq 38^{\circ}\text{C}$  ( $\geq 100.4^{\circ}\text{F}$ ), postpone vaccination until the condition is resolved.
- 7) Contact IRT system for vaccine assignments.
- 8) Administer the following study vaccines. Each vaccine should be administered in an assigned location and documented appropriately (see Operating Guidelines).
  - Meningococcal vaccine (MenACYW conjugate vaccine or MENVEO®): inject IM into the anterolateral area of the thigh, preferably the right thigh.
  - Pentacel®: inject IM into the anterolateral area of the thigh, preferably the left thigh (i.e., the opposite leg from that used for meningococcal vaccine administration.)
  - Havrix®: inject IM into the anterolateral area of the thigh, preferably the left thigh (i.e., the opposite leg from that used for meningococcal vaccine administration).

When multiple vaccines are administered at a single visit, each vaccine should be administered at a different anatomic site. If vaccines are given in the same limb, the injection sites should be separated by 1 inch or more so that any local reactions can be differentiated.

Failure to administer vaccines in the designated limb will not constitute a protocol deviation, but should be recorded as a comment in the CRF.

- 9) Observe the subject for 30 minutes and record any AEs in the source document. In the event of a local reaction, indicate the associated vaccine.
- 10) Give the parent / guardian a diary card (DC6).
- 11) Remind the parent / guardian to expect a telephone call 8 days after Visit 6 and to bring back the diary card when they return for Visit 7 at a specified date and time.

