4.4.2.2 Unsolicited AEs

4.4.2.2.1 Presence

An observation will be considered an event if it has at least a verbatim term and is not Grade 0 (None) intensity event.

Grade 0 events are not included in safety analysis but are included in separate listings.

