4.4.2.5.5 AEs Leading to Study Discontinuation

This information will be summarized as collected. A flag is available in the clinical database for all AEs in order to identify AEs leading to Discontinuation.

In general, the items that are counted are:

- Disposition table: A subject who on the “Completion at End of Study” form
- Question “What was the participant's status?” has “Adverse Event” checked.
- Safety overview table: A subject who either on the “Completion at End of Study” form, question “What was the participant's status?” has “Adverse Event” checked or lists a solicited AE that has “Caused Study Termination” checked that is at least Grade 1 or an unsolicited AE that has “Caused Study Discontinuation” checked that is at least Grade 1 or missing and is within the time period indicated.
- System Organ Class/Preferred Term (SOC/PT) table: A solicited AE that has “Caused Study Termination” checked that is at least Grade 1 or an unsolicited AE that has “Caused Study Discontinuation” checked that is at least Grade 1 or missing and is within the time period indicated.

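### For non-fever solicited reactions the SAP uses an investigator's 'No' when all daily records are missing but has no step for 'Yes', so occurrence is biased downward, probably by little

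*SAP*

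**What the plan says.** SAP 4.4.2.1.1 derives daily intensity in two steps. The first, from which fever is exempt, applies when the investigator answered 'No' to presence: "with all daily records missing, then all daily intensities will be derived as None". Such a child has no presence and remains in the denominator. The second step relies on what was recorded day by day: for reactions that are not measured, "daily intensities will correspond to daily records reported in the clinical database", and measured reactions are converted by the intensity scale. Neither step says what to do when the investigator recorded 'Yes' and no daily record exists.

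SAP 4.4.2.1.3 takes presence from the maximum intensity alone. An unknown maximum gives a missing presence, and "those without a non-missing presence will not be included in the analysis of the endpoint". SAP 5.4.1.3, on missing intensities, only points back to 4.4.2.1.1.

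Unsolicited events are handled differently. Under SAP 4.4.2.2.1, "An observation will be considered an event if it has at least a verbatim term" and is not Grade 0, so a missing grade does not remove it.

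SAP 4.4.2.5.5 separates the two kinds of event again. In the safety overview and the SOC/PT table, a solicited reaction qualifies if its termination box is "checked that is at least Grade 1 or an unsolicited AE that has" the corresponding discontinuation box ticked. For the unsolicited half a missing grade is also accepted; for the solicited half it is not.

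**The concern.** The same collected field settles the result when it says there was no reaction and has no role when it says there was one. Dropping children with unknown outcomes need not bias a rate. Dropping only the reported reactors, while keeping the reported non-reactors, must.

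Solicited reactions are the core of the reactogenicity description, and whether a reaction led to early termination is part of the endpoint (Protocol 9.3.2.2, SAP 4.3.2.2). At stake is a modest understatement of non-fever solicited reaction rates in infants, and a terminating reaction that could be missing from the table giving its preferred term.

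**Working it through.** The plan states no figure on this point, so there is nothing to reproduce. The check is to trace the rules and then size the effect.

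**Tracing a child with every daily record missing for one reaction**

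| Investigator field | Non-fever reaction | Fever |
|---|---|---|
| 'No' | None; kept as a non-reactor | Unknown; dropped |
| 'Yes' | Unknown; dropped | Unknown; dropped |

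The imbalance is in the non-fever column only. Fever is exempt from the first step, so both answers are dropped. The handling of 'Yes' is inferred from the absence of a step; no sentence says that a 'Yes' is discarded.

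**Direction.** Take N children, x with the reaction, and k of those with 'Yes' and no daily record. The reported rate is (x − k)/(N − k). This is below x/N whenever k > 0 and x < N, because N(x − k) < x(N − k) reduces to xk < Nk.

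**Size.** Let p be the true rate and u the share of reactors affected. The documents give neither, so both are assumptions. Non-reactors with no daily records are taken to carry a 'No'.

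Reported rate = p(1 − u)/(1 − pu)

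| p | u = 1% | u = 5% | u = 10% |
|---|---|---|---|
| 10% | 9.91% | 9.55% | 9.09% |
| 30% | 29.79% | 28.93% | 27.84% |
| 50% | 49.75% | 48.72% | 47.37% |
| 70% | 69.79% | 68.91% | 67.74% |

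The understatement runs from 0.09 to 2.63 points. For scale, with the planned 1752 children in Group 1, p = 50% and u = 5%, 1752 × 0.50 × 0.05 = 43.8, so about 44 reactors would be dropped.

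**Is the asymmetry the cause?** If reactors and non-reactors with no records were both dropped at 5%, the rate would be p(1 − 0.05)/(1 − 0.05p − 0.05(1 − p)) = p. That recovers 30% and 50%, against 28.93% and 48.72% under the rule as written.

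**Group difference at p = 50% in both groups**
- u = 5% in both: no shift.
- u = 5% against 0%: a shift of −1.28 points.
- u = 10% against 2%: a shift of −2.13 points.

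**Extending a 'Yes' rule to fever.** Assume a true fever rate of 20% and 5% of children, reactors and non-reactors alike, with no temperature record. As written, both are dropped and the rate stays at 20.0%. If 'Yes' were kept while 'No' was still dropped, the rate would be 0.20/(0.20 + 0.80 × 0.95) = 0.20/0.96 = 20.8%, an upward bias.

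**The case against.** The strongest reply is that the situation is rare and already controlled. It needs every daily record for that reaction to be missing; one graded day restores presence. A measured reaction too large to measure is set to Grade 3, so it is not lost. Parents are called at day 8 and reminded to complete the card (Protocol 5.1.4.1), missing diary entries are to be clarified verbally and entered (Protocol 13.2), and the investigator must account for missing data (Protocol 11.1). This stands: the effect is probably small. It does not close the gap, since a parent may recall a reaction but not its daily grade.

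The sponsor may add that recorded measurements deliberately outrank the investigator's flag (the note in SAP 4.4.2.1.1, and 4.4.2.1.7). That explains overriding a 'Yes' when measurements exist. Here none exist, and the first step already relies on the investigator in that case.

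A reader might go further in three ways that the documents do not support.

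- **A bias between the vaccines.** After Visit 5, Subgroups 1a and 2a return the diary 30 to 51 days later. In 1b the instruction to "Collect and review the diary card (DC5) with the parent / guardian" comes only at 15 to 18 months of age, and 2b has the same timing. More lost records in 1b and 2b is plausible but undocumented. Each MenACYW subgroup also has a MENVEO subgroup with the same pattern of diary review, and both groups are split 2:1.
- **Children leaving the safety analysis.** The child leaves only that reaction's analysis. The safety set and the rows for other reactions are unaffected.
- **Terminating reactions vanishing altogether.** Protocol 5.2.10 makes an adverse event the recorded reason when a child is permanently terminated because of one. Under SAP 4.4.2.5.5 that entry alone places the child in the disposition and overview tables. The SOC/PT table is the one exposed.

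**Conclusion.** The point holds for solicited reactions other than fever. Following the SAP as written, a reported but wholly ungraded reaction leaves that endpoint's numerator and denominator, while a reported absence with no records is kept, so occurrence is biased downward. The direction follows from the text, given that no step handles 'Yes'. The size does not: 0.1 to 2.6 points is the range under assumed shares of 1% to 10% of reactors and rates of 10% to 70%, and the diary controls favour the lower end. A shift between groups needs unequal shares or rates, for which the documents give no evidence.

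The discontinuation gap rests on explicit wording and is confined in practice to the SOC/PT table. It would be a mistake to read fever as sharing the defect, because fever already treats 'Yes' and 'No' alike. Safety is descriptive (SAP 5.1.4), so no hypothesis test depends on this. A clarification before analysis is still warranted, because it uses a field that the SAP already reads.

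**What to change.** - In SAP 4.4.2.1.1 and 4.4.2.1.3, add: *For solicited reactions other than fever, if investigator presence is Yes and all daily records are missing, Presence is Yes and maximum intensity is Missing. The child is included in the denominator and in the 'any' row, and is shown in a Missing-intensity row.*
- Leave the fever derivation unchanged. Report, per group, the number of children with fever presence 'Yes' and no daily record.
- In SAP 4.4.2.5.5, in the overview and SOC/PT bullets, change the solicited criterion to accept Grade 1 or higher or a missing grade, as already written for unsolicited events.

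The cost is a few SAP sentences and one extra row in the solicited tables, with no new data collection. The downside is that a few ungraded reactions enter the 'any' row, so reported rates become slightly less favourable.

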4.4.2.1.4 Time of Onset

Time of onset is derived from the daily intensities as described in [Section 4.4.2.1.1](#). It corresponds to the first day with intensity of Grade 1, Grade 2, or Grade 3.

Note: If a reaction is not continuous (i.e., reaction occurs over two separate periods of time intervened by at least one daily intensity Missing or None) then the time of onset is the first day of the first occurrence.

Time of onset period is displayed as, D0-D3, D4-D7.

4.4.2.1.5 Number of Days of Occurrence during the solicited period

Number of days of occurrence over the solicited period (D0 to D7) after each vaccination is derived from the daily intensities as described in [Section 4.4.2.1.1](#). It corresponds to the number of days with one of daily intensities of Grade 1, Grade 2, or Grade 3. Number of days of occurrence on the solicited period with a specified intensity (e.g., Grade 3) may also be derived.

4.4.2.1.6 Overall Number of Days of Occurrence

If a reaction is ongoing at the end of the solicited period, then the overall number of days of occurrence after each vaccination is derived from the daily intensities and the stop date of the reaction after the end of the solicited period. The overall number of days of occurrence is:

$$(\text{End date of the solicited event} - \text{last vaccination date}) + (\text{number of days of occurrence within the solicited period}) - \text{length of the solicited period} + 1$$

If the end date of the solicited reaction is missing or is incomplete (contains missing data), then the overall number of days of occurrence will be considered as Missing.

4.4.2.1.7 Ongoing

Ongoing is derived from the last daily intensity of the solicited period as described in [Section 4.4.2.1.1](#) and the maximum intensity on the ongoing period after each vaccination. The investigator's ongoing flag is not used because the measurement would determine the ongoing status of the reaction.

- Ongoing: if the last daily intensity of the solicited period is at least Grade 1 and the maximum intensity on the ongoing period is at least Grade 1
- Not ongoing: if the last daily intensity of the solicited period is None or the maximum intensity on the ongoing period is None.
- Missing: all other conditions (in this case, it is not included in the denominator of the ongoing analysis in the safety tables)

4.4.2.2 Unsolicited AEs

4.4.2.2.1 Presence

An observation will be considered an event if it has at least a verbatim term and is not Grade 0 (None) intensity event.

Grade 0 events are not included in safety analysis but are included in separate listings.

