By definition, solicited reactions are to be considered as being related to the product administered. The assessment of these reactions by the Investigator is mandatory. For injectable vaccines, solicited reactions can either be solicited injection site reactions or solicited systemic reactions.

Unsolicited AE / AR:

An unsolicited AE is an observed AE that does not fulfill the conditions prelisted in the CRB in terms of diagnosis and/or onset window post-vaccination. For example, if headache between D0 and D07 is a solicited reaction (i.e., pre-listed in the protocol and CRB), then a headache starting on D07 is a solicited reaction, whereas headache starting on D08 post-vaccination is an unsolicited AE. Unsolicited AEs includes both serious (SAEs) and non-serious unsolicited AEs.

Injection Site Reaction:

An injection site reaction is an AR at and around the injection site. Injection site reactions are commonly inflammatory reactions. They are considered to be related to the product administered.

Systemic AE:

Systemic AEs are all AEs that are not injection or administration site reactions. They therefore include systemic manifestations such as headache, fever, as well as localized or topical manifestations that are not associated with the vaccination or administration site (e.g., erythema that is localized but that is not occurring at the injection site).

Adverse Event of Special Interest (AESI):

AESI is an event for which ongoing monitoring and rapid communication by the Investigator to the Sponsor must be done. Such an event might warrant further investigation in order to characterize and understand it. Depending on the nature of the event, rapid communication by the study Sponsor to other parties (e.g., regulators) might also be warranted.

Medically-Attended Adverse Event (MAAE)

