An MAAE is defined, for the purpose of this study, as a new onset of a condition that prompts the subject or subject's parent/guardian to seek unplanned medical advice at a health care provider's office or Emergency Department. This definition excludes pre-planned medical office visits for routine pediatric check-ups or follow-up visits of chronic conditions with an onset prior to entry in the study. Health care provider contact made over the phone or by email will be considered a physician office visit for the purpose of MAAE collection. The outcome of the health care provider contact (whether it results in a prescription or not) will not be considered as a basis for reporting the event as an MAAE and all contacts should be reported. Sufficient data should be collected for the event to allow an assessment of the causality and diagnosis, if possible.

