4.4.2.2.2 Intensity

Intensity will be derived according to the following classification:

None, Grade 1, Grade 2, Grade 3, or Missing (Unknown).

If the unsolicited AE is measurable and its preferred term is part of the list of solicited reactions, then the measurement is derived based upon and following the same rule as the intensity scales defined in the [Section 4.4.2.1.1](#) for that measurable injection site or systemic reaction. Note the intensity could be considered as "None" (not a reaction) in the analysis despite being considered a reaction by the investigator.

Intensity for the other unsolicited non-serious AEs will correspond to the value reported in the CRF. The maximum intensity corresponds to the highest intensity for a unique term.

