4.4.2.2.4 Time of Onset

Time of onset is derived from the start date of the unsolicited AE and the date of last vaccination as described in [Section 4.4.2.2.3](#):

Time of Onset = start date of the unsolicited AE - date of last vaccination before the unsolicited AE.

The time of onset is considered as missing only if one or both dates are missing or partially missing.

The unsolicited AEs will be analyzed “Within 30 days” after each vaccination, which corresponds to AEs with a time of onset between day 0 and day 30.

Unsolicited AE that occurred before vaccination (negative time of onset) will not be included in analysis but will be listed separately.

Unsolicited AE which is non-serious, non-AESI and non-MAAE that occurred with a time of onset higher than defined above will not be included in analysis but will be listed separately.

- For unsolicited AE with missing day, month and year, the unsolicited AE will be classified as “Within 30 days”
- For unsolicited AE with partially missing start date, the partial available information will be used to determine if this AE is classified “Within 30 days” or “Not within 30 days”. An AE will be categorized as “Not within 30 days” only if there is clear evidence from the partially missing start date that this AE happens before the first vaccination or after the last vaccination + 30 days. In all other situations, this AE is considered as “Within 30 days”. Situations may happen as:
 - If the start date of AE has missing Day and non-missing Month and Year:
 - If the “Month/Year of AE start date” < “Month/Year of first vaccination date”, then it is clear that this unsolicited AE happened before the first vaccination and this unsolicited AE will not be included in the analysis but will be listed separately.
 - Else if the “Month/Year of last vaccination date” <= “Month/Year of AE start date” <= “Month/Year of (last vaccination date + 30 days)”, then this unsolicited AE will be categorized as “Within 30 days”.
 - Else if the “Month/Year of AE start date” > “Month/Year of (last vaccination date + 30 days)”, then this unsolicited AE will be categorized as “not within 30 days”. If the AE is non-serious, non-AESI and non-MAAE, then it will not be included in the analysis but will be listed separately.
 - If the start date of AE has missing Day and Month and non-missing Year:

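### The SAP's exclusion of Grade 0 unsolicited events has no exemption for medically-attended or serious events, and the SAP does not say whether it overrides the sections that promise to analyse all of them

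*SAP*

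**What the plan says.** **The exclusion.** SAP 4.4.2.2.1 (Presence) sets the entry condition for unsolicited AEs: "An observation will be considered an event if it has at least a verbatim term and is not Grade 0 (None) intensity event". It then gives the consequence: "Grade 0 events are not included in safety analysis but are included in separate listings". The section has no exception.

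**How Grade 0 arises.** SAP 4.4.2.2.2 (Intensity) applies the solicited-reaction scale under this condition: "If the unsolicited AE is measurable and its preferred term is part of the list of solicited reactions". It accepts that the derived intensity may be None "despite being considered a reaction by the investigator". SAP 4.3.2.3.3 confirms that temperature for an unsolicited fever is analysed on the solicited scale. That scale starts at 38.0°C (SAP Table 4.2, protocol Table 9.2).

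**Who is inside the rule.** SAP 4.3.2.1 states: "Unsolicited AEs includes both serious (SAEs) and non-serious unsolicited AEs". SAP 4.3.2.3.5 has MAAEs recorded as unsolicited AEs up to D30 after each vaccination. The MAAE definition in 4.3.2.1 rests on unplanned medical contact for a new condition and sets no intensity threshold; on such contacts it says "all contacts should be reported".

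**What points the other way.** SAP 4.4.2.3 and 4.4.2.4 classify SAEs, AESIs and MAAEs by a CRF box alone, and their whole-study analysis period covers all SAEs and all MAAEs. Protocol 12.1.3 commits to the number and percentage of subjects with at least one MAAE of any kind.

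**The concern.** Intensity grading on the solicited scale is a reactogenicity convention. An MAAE is defined by the health-care contact and an SAE by seriousness criteria, so a temperature cut-off should not decide whether either is counted.

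The authors saw this problem in a neighbouring rule. The late-onset exclusion in 4.4.2.2.4 is confined to an "Unsolicited AE which is non-serious, non-AESI and non-MAAE that occurred with a time of onset higher than defined above", which keeps SAEs, AESIs and MAAEs in the analysis. The Grade 0 rule has no such wording.

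Two programmers could follow this SAP faithfully and produce different MAAE counts. MAAEs are a named safety endpoint over the whole study in infants and toddlers, so the count should not rest on an unrecorded programming choice.

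**Working it through.** There is no power figure or event count in the plan to reproduce. The check is a hand trace of unsolicited records through the rules.

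**Step 1: which records can become Grade 0** (SAP Tables 4.1 and 4.2; sections 4.3.2.3.3, 4.4.2.2.1 and 4.4.2.2.2)

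| Unsolicited record | Derived intensity | Under 4.4.2.2.1 |
|---|---|---|
| Pyrexia, 37.9°C | None | Not an event; listed only |
| Pyrexia, 38.0°C | Grade 1 | Analysed |
| Pyrexia, temperature missing | Missing | Analysed |
| Injection site erythema or swelling, above 0 mm | Grade 1 or higher | Analysed |
| Injection site erythema or swelling, 0 mm | None | Listed only |
| AE not re-graded from a measurement | Grades 1 to 3 only | Analysed |

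In practice the rule reaches measured fever below 38.0°C and little else. It also has an odd result: a fever report with no temperature stays in, while the same report with 37.9°C goes out.

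**Step 2: the onset window.** Fever with onset from D0 to D7 is a solicited reaction (SAP 4.3.2.1), so this unsolicited-AE rule does not govern it. The exposed records are fever reports with onset after D7.

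**Step 3: the same 37.9°C record with the MAAE box ticked.**

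- If 4.4.2.2.1 governs, it is not an event and is only listed.
- If 4.4.2.4 governs, it is an MAAE and is counted.

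**Step 4: does the text settle the order of the two rules?**

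- For counting: 4.4.2.3 and 4.4.2.4 stand at the same level as 4.4.2.2, carry no grade condition, and cover all SAEs and all MAAEs.
- For excluding: both sections classify an event, and 4.4.2.2.1 reserves that word for observations that are not Grade 0. The exemption written into 4.4.2.2.4 is absent from 4.4.2.2.1.
- The SAP does elsewhere apply a grade filter to a category defined by outcome. In 4.4.2.5.5 an unsolicited AE that caused discontinuation enters the SOC/PT table only if it is at least Grade 1 or missing.

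Nothing in either document ranks the two rules.

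**Step 5: size.** The number of affected MAAE reports would be 2628 children × medically-attended fever reports per child with onset after D7 × the share of those with a recorded temperature below 38.0°C. Only the first factor is in the documents. I give no range, because any values for the other two would be invented.

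**The case against.** The strongest reply is that the SAP already protects these events. Sections 4.4.2.3 and 4.4.2.4 use the CRF box, promise analysis of all SAEs and MAAEs, and match protocol 12.1.3. This stands in part. A reader might infer from 4.4.2.2.1 alone that qualifying MAAEs and SAEs are definitely dropped and under-counted. The documents do not support that; they support an unresolved conflict. The reply does not remove the conflict, for the reasons in step 4.

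Other points on that side, and what stands:

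- **SAEs.** To be lost, an SAE would have to be coded to a re-graded term, in practice pyrexia, with a measured temperature below 38.0°C and outside the solicited window. A seizure, or a hospitalisation coded to a diagnosis, is not re-graded. The SAE endpoint and the SAE row of Table 5.5 do not use intensity. This stands: the SAE part is close to theoretical.
- **Below 38.0°C is not fever under the protocol.** True, but the MAAE definition turns on the contact, not the reading.
- **A low reading after an antipyretic.** Maximum intensity is the highest for a term, and for diary temperatures the site records the highest. One low reading therefore does not decide the grade if a higher one was recorded. This stands and narrows the reach further.
- **Discontinuations.** The disposition and overview tables already count a subject whose completion form gives an adverse event as the reason, whatever the grade. Only the SOC/PT table is exposed.
- **Consequence.** Safety is observational with no hypothesis tested, the rule is the same in both groups, excluded records remain in listings, and a child with another counted MAAE still contributes to the subject percentage. All of this stands and keeps the point small.

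**Conclusion.** The point holds as a contradiction between stated rules, not as a demonstrated loss of events. SAP 4.4.2.2.1, read with 4.4.2.2.2, would move a medically-attended report of unsolicited fever measured below 38.0°C out of the MAAE analysis; 4.4.2.4 and protocol 12.1.3 would count it; and the SAP does not say which prevails. If 4.4.2.2.1 governs, a report that meets the MAAE definition appears only in a listing.

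The reach is narrow, and no primary or secondary conclusion depends on it. Its size cannot be computed from the documents. A reader might want to state a number of lost MAAEs, or to say that SAEs are under-counted. The first would rest on rates the documents do not give, and both would presume the reading of the SAP that is in dispute.

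The conclusion assumes that an unsolicited fever report can be flagged as an MAAE in the CRF while carrying a recorded temperature below 38.0°C. Nothing in the documents prevents this, and rectal measurement is only the preferred route. It is worth correcting because it can change a named safety endpoint and the remedy is already in the SAP's own wording for late-onset events.

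**What to change.** In SAP 4.4.2.2.1:

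- Limit the Grade 0 exclusion to events that are non-serious, not AESIs, not MAAEs and did not lead to discontinuation, following the pattern of 4.4.2.2.4.
- State that records flagged as SAE, AESI or MAAE are counted whatever the derived intensity, with None displayed as below Grade 1.
- Cross-refer to 4.4.2.3 and 4.4.2.4 so that the order of the rules is explicit.

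In SAP 4.4.2.5.5, align the SOC/PT discontinuation table with this rule. The disposition and overview tables need no change for these subjects, since they already count them through the completion form.

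The cost is a sentence or two in the SAP and one programming filter. The downside is that a few medically-attended reports with temperatures below 38.0°C will appear in the tables; the below-Grade-1 label lets a reader recognise them.
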